Official Study Title: Detecting Neonatal Hypoglycemia Using Real-Time Continuous Glucose Monitoring (CGM)

NCT Number: NCT03032523

Date of Document: 3/6/2019

PROTOCOL

TITLE

Detecting Neonatal Hypoglycemia using Real-Time Continuous Glucose Monitoring (CGM)

SUMMARY

Newborn infants have many complex physiological changes taking place that are difficult to anticipate. Infants born to mothers who have diabetes during their pregnancy are especially vulnerable to hypoglycemia. Our study will evaluate blood sugar changes during the first few days of life and the utility of CGM systems to detect clinically significant hypoglycemia in infants. This randomized, controlled single-blind trial will compare infants on CGM alone versus those using CGM who are remotely monitored by a physician through the Dexcom Share application. The number of hypoglycemic events that are detected in each group will be compared. For each time point that the unblinded CGM group has a low blood sugar level, it will be verified by standard heelstick (capillary) measures. Finally, the sensitivity and specificity of detecting hypoglycemia in the infant will also be determined.

INCLUSION CRITERIA

- Participants must be born at 34 weeks gestation or later
- Participants must be admitted Lucile Packard Children's Hospital
- Infants born at outside hospitals and transferred to LPCH will be eligible for the study
- Mothers have a diagnosis of pre-gestational diabetes
- Mothers with gestational diabetes have poorly controlled gestational diabetes defined as elevated Hemoglobin A1c (greater than 6%) during pregnancy or hyperglycemia based on home glucometer readings while pregnant. This includes fasting or pre-prandial blood glucose values of greater than 100 mg/dl, post-prandial blood glucose values greater than 140mg/dl at 1 hour or greater than 120mg/dl at 2 hours consistently.
- Any mothers who require insulin, metformin, or glucose lowering medications during gestation

EXCLUSION CRITERIA

- Infants <2,000g will be excluded from the study.
- If infants receive Acetaminophen, sensor readings will not be included in the analysis for 6 hours after the medication is given because this medication may falsely raise the sensor's glucose readings.
- Infants will also be excluded if they have an anomaly of the skin or subcutaneous tissue that would prevent proper adhesion, placement, and function of the sensor.

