 - Using the Dexcom Follow Application, auditory and vibratory alerts will be enabled for blood glucose values <46 mg/dl or signal loss for >60 minutes and sent directly to the study physician remotely monitoring participants.
 - Signal loss of greater than 3 hours will require participants to have a new subcutaneous sensor inserted and the initial calibration steps will need to be repeated.
- Dexcom Receivers and Ipods will remain connected to a power source as much as possible during the study period.

DEXCOM CGM PROTOCOL: Calibration

- After the initial 2 hour start-up period, the sensor will be calibrated using two successive capillary blood glucose measurements using a study glucometer.
- The same type of device will be used for all capillary blood glucose measurements performed on the infant.
- For each capillary blood glucose sample, an area of skin will be cleansed, allowed to dry, pricked using a sterile lancet, and the smallest amount of blood possible will be used for proper testing.
- Every effort will be made to ensure capillary blood glucose levels are checked at least every 12 hours from the time of initial calibration until the time of discharge or 7 days of life, whichever comes first.
- Glucose levels will be entered into the transmitter for calibration within 5 minutes of obtaining the glucose measurement.
- In the remote monitoring group, a trained study staff member will work with nursing staff to perform and input the calibration measurements into the receiver.

MONITORING FOR HYPOGLYCEMIA

- When the monitoring physician receives an alert for a low glucose value <46 mg/dl, they will contact the nurse taking care of the patient. First, the infant will be assessed to see if excess pressure is being placed on the sensor due to positioning. If so, the infant may be repositioned and monitored to see if the glucose values rise above 45mg/dl. If CGM glucose values remain low, a bedside glucose reading will be performed. This value will be recorded in the chart and by the monitoring physician in the study. Based on the standard of care blood glucose reading, the staff will take appropriate measures based on the standard of care (see appendix).
- If the hypoglycemia alarm continues for an additional 60 minutes, the nurse caring for the patient will be prompted to obtain an additional standard of care blood glucose measurement.

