Maternal data, including mother's age, pregnancy history, type of diabetes, and treatment of diabetes during pregnancy were collected. Neonatal characteristics collected included sex, race, ethnicity, gestational age, birth weight, type of delivery, and other risk factors for hypoglycemia. Perinatal stressors were defined as an Apgar score <7, admission to NICU, or treatment of the infant beyond the usual suctioning and stimulating that routinely occurs after birth.¹⁴ Prematurity was defined as birth at <37 weeks gestation. Small for gestational age (SGA) infants weighed less than the 10th percentile for gestational age, whereas large for gestational age (LGA) infants weighed greater than the 90th percentile for gestational age.

Power calculation

Using an older retrospective CGM device in a similar cohort of at-risk infants, Harris found that using similar SOC intermittent heel-stick glucose monitoring, 32% of infants had glucose levels <47 mg/dL.¹⁵ We estimated that in our cohort, the SOC would find 32% of these high-risk infants with glucose levels <47 mg/dL. We estimated that with a sample size of 40, we should be able to detect a higher CGM rate of hypoglycemia of *57% (80% power, alpha = 0.05, one sided). However, because we were unable to recruit 40 infants during the time frame of the randomized trial, we modified the study design; instead, our goal was to determine if there was additional benefit of using CGM monitoring to detect hypoglycemia missed by SOC testing and to determine the false-positive rate of CGM alerts for hypoglycemia.

Outcome measures

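### Alerts that clear after repositioning have no required reference test, contrary to the Summary, and the plan does not say how they enter the false-positive rate or the PPV

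*Combined protocol and SAP*

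**What the plan says.** The Summary gives a rule for reference testing without exceptions: "For each time point that the unblinded CGM group has a low blood sugar level, it will be verified by standard heelstick (capillary) measures". I take the unblinded group there to be the remotely monitored infants, because theirs are the readings sent to the study physician.

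Monitoring for Hypoglycemia sets out a sequence instead. An alert below 46 mg/dl leads the monitoring physician to call the bedside nurse, and the position of the infant is checked for pressure on the sensor. The next step is conditional and optional: "If so, the infant may be repositioned and monitored to see if the glucose values rise above 45mg/dl". The reference test comes only after that, and it too is conditional: "If CGM glucose values remain low, a bedside glucose reading will be performed". A further reading is prompted if the alarm goes on for another 60 minutes. The bedside glucose value is the one item in this sequence that the monitoring physician is told to record.

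Apart from alerts, the Calibration section provides for routine checks: "Every effort will be made to ensure capillary blood glucose levels are checked at least every 12 hours from the time of initial calibration".

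Under Data Analysis, the Power calculation subsection explains that 40 infants could not be recruited and that the aim was changed. Two goals remain: the added detection of hypoglycemia missed by standard of care, and "to determine the false-positive rate of CGM alerts for hypoglycemia". Outcome measures lists the PPV as a secondary outcome and defines hypoglycemia as a glucose below 45 mg/dL. Neither subsection gives a numerator, a denominator or a rule for alerts without a glucometer value.

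**The concern.** Whether an alert gets a reference test depends on what the sensor shows next, after a step meant to catch artefacts. This is partial verification: the alerts that the plan itself has reason to suspect are the ones least likely to be tested. Each of them still reached the physician and led to a call and a bedside assessment, so a reader would expect them to count when the burden of false alerts is reported.

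A false-positive rate or PPV that needs a glucometer result will lose them unless the plan says otherwise, and the likely error favours the device. The point concerns the alert-based measures, not the primary count of events.

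**Working it through.** The plan states no alert count, false-positive rate or PPV, so it has no figure of its own to reproduce here. Its sample size of 40 belongs to the abandoned comparison and plays no part.

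**Step 1. The two rules side by side.**

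| Course of the alert | Summary | Monitoring for Hypoglycemia |
|---|---|---|
| No pressure found, CGM still low | heelstick | bedside glucose (natural reading) |
| Pressure found, CGM stays low | heelstick | bedside glucose |
| Pressure found, infant repositioned, CGM rises above 45 mg/dl | heelstick | none required |

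The rules differ in the last row.

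**Step 2. Notation.** I read the false-positive rate of alerts as the share of alerts that are false, the complement of an alert-based PPV. Let A be the alerts confirmed by glucometer, B those refuted, and C those that cleared with no time-matched glucometer value. Then:

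- c = C/(A+B+C), the cleared share
- f = B/(A+B), the false share among tested alerts
- q = the false share among cleared alerts, which cannot be observed

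The documents give none of c, f or q, so every value below is assumed.

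**Step 3. Formula.** The rate over all alerts is (1−c)f + cq. The error of the tested-only rate is f − [(1−c)f + cq] = c(f−q). It is too low if q > f, unbiased if q = f, and too high if q < f.

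**Step 4. All-alert rate if every cleared alert is false (q = 1).**

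| Tested-only rate f | c = 10% | c = 20% | c = 30% | c = 40% |
|---|---|---|---|---|
| 30% | 37% | 44% | 51% | 58% |
| 50% | 55% | 60% | 65% | 70% |
| 70% | 73% | 76% | 79% | 82% |

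For example, f = 50% and c = 30% give 0.70 × 0.50 + 0.30 × 1 = 0.65. The tested-only rate is too low by 7 to 28 points at f = 30%, 5 to 20 at f = 50%, and 3 to 12 at f = 70%.

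**Step 5. Sensitivity to q.** With f = 50% and q = 80%, the all-alert rate is 53%, 56%, 59% and 62% across the same values of c. With f = 90%, q = 80% and c = 30%, it is 0.70 × 0.90 + 0.30 × 0.80 = 0.87, so the tested-only rate is 3 points too high.

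**Step 6. Bounds that need no assumption about q.** Setting q = 0 and q = 1 gives B/(A+B+C) and (B+C)/(A+B+C), an interval of width c. For 100 alerts with A = 35, B = 35 and C = 30, the tested-only rate is 35/70 = 50% and the bounds are 35% and 65%.

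**The case against.** A reader might infer that cleared alerts are never tested, that the false-positive rate rests only on the surviving alerts, and that it therefore comes out too low. The documents do not support any of the three in that form.

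- *Never tested.* No heelstick is triggered by a cleared alert, but 12-hourly checks and standard-of-care tests continue, and one may fall nearby by chance. The affected group is also limited: pressure must be found, repositioning is optional, and the CGM value must then rise.
- *Only the surviving alerts.* The plan states no denominator. The sponsor might drop cleared alerts, count them as false or report them separately. What the text supports is an undefined denominator.
- *Too low.* This requires that cleared alerts be dropped and that q exceed f. The second is likely, but no data in the documents establish it. The monitoring period after repositioning has no time limit, so a true brief low could recover while being watched.

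It can also be said that a rate among alerts that survive an artefact check is a legitimate measure. I agree, provided that it is labelled so.

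These objections limit the claim about direction and size. They leave the conflict between the two sections and the missing rule untouched. Dropping cleared alerts or counting them all as false changes the result by c(1−f), which is 5 to 20 points at f = 50% and c from 10% to 40%. A stated goal should not hang on an unstated choice.

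**Conclusion.** The Summary and Monitoring for Hypoglycemia contradict each other on which lows are verified, and the sponsor must reconcile them. I take no view on which clinical rule should stand. Under the monitoring section, cleared alerts have no required reference value and no required record of why they cleared, and the plan does not say how they enter the false-positive rate or the PPV.

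If they are dropped, the false-positive rate is probably too low and the PPV too high. The contradiction and the missing rule are certain on the text, the direction is likely, and the size is unknown. The ranges in the working rest on assumed values of c and f and, in the main table, on q = 1. Because the primary event count is unaffected and a definition with bounds closes the gap, I rate this as should-fix.

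**What to change.** Reconcile the two sections on whether every low is verified. For the analysis:

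1. Make the alert the unit. Classify each as A (confirmed by glucometer), B (refuted by glucometer) or C (cleared, no time-matched glucometer value). State the matching window and the glucometer cut-off, since alerts fire below 46 mg/dl while the outcome definition is below 45 mg/dL.
2. Report the number in C.
3. Report B/(A+B), labelled as applying to alerts that reached a heelstick.
4. Report the all-alert bounds B/(A+B+C) to (B+C)/(A+B+C). Present neither as the headline, because the upper bound treats untested alerts as proven false and the lower treats them as proven true.
5. Give the PPV on the same denominators: A/(A+B), with bounds A/(A+B+C) to (A+C)/(A+B+C).

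The classification can come from a record kept by the monitoring physician. The Data Analysis text is in the past tense, so collection may be finished. In that case it can be built from the CGM files and charts, although the CGM files will show that a low resolved and not why.

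The cost is some data work, one added analysis paragraph, and a wider and probably less favourable false-positive figure. The analysis fix requires no extra heelsticks and no change to bedside care.

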- If the measurement at 60 minutes shows that the patient has a BG >45mg/dl, the CGM may be re-calibrated (see below).
- In the case of severe hypoglycemia (BG <35mg/dl) found in both control and experimental groups during routine calibration procedures will require that the clinical staff caring for the patient be notified to ensure safety of the patient.
- For all blood glucose measurements that are >20% different from the Dexcom CGM values in the experimental group, a blood glucose test may be performed to re-calibrate the sensor prior to the 12 hours. Sensor re-calibration will only occur between glucose values of 40 mg/dl and 400 mg/dl based on manufacturer guidelines.

MONITORING FOR SENSOR SITES FOR INFECTION

- Sensor sites will be assessed at least once per 12 hour nursing shift and as needed during nursing cares for the duration of the study.
- Evidence of inflammation (redness, swelling, discharge) will be documented and discussed with the clinical care and research team.
- If the sensor site is thought to be infected, the sensor will be removed immediately and appropriate steps will be taken to treat the infection by the clinical team managing the patient.

RISKS ASSOCIATED WITH CGM USE

When the needle and sensor are inserted, the child should expect to experience a small amount of pain for a few seconds. After insertion, your child may or may not feel some tenderness or pain.

Pain, inflammation or redness, swelling, minor infection, and minor bleeding at the sensor insertion site are possible risks with your child's use of the study device. In extremely rare cases an infection might spread to other parts of the body. Significant or serious health risks with the investigational device are not anticipated.

Minor irritation may occur where the adhesive pad is placed. This will occur in most research participants and should clear up within hours to not more than a week after removal. The child may experience some itching in the area during the healing process, which is normal. The child may develop an allergic reaction to one or more parts of the sensor and transmitter. This is similar to allergies that occur due to medical tape or jewelry. Allergic reactions will usually be mild and require only a skin cream to make them better. Severe allergic reactions are rare. If the child has an allergic reaction, study staff should be notified.

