On rare occasion, the sensor may cause skin injury and tissue trauma known as medical adhesive-related skin injury (MARS). If this happens, study staff should be notified as soon as possible.

There is a chance that the sensor or needle may break during use of the device. This is not expected to occur; but, if it does, the study staff should be contacted about what to do. They will see if the child has symptoms of infection or inflammation, swelling, redness, or pain at the insertion site. Treatment will be provided if needed. If a sensor breaks, it may be left under the skin indefinitely as long as no portion of the wire sensor fragment is visible above the skin and there are no symptoms of infection, redness, and/or swelling.

The radio waves that the transmitter puts out will not hurt the family or their child, nor will the child be aware of them.

EVALUATION AND TREATMENT OF HYPOGLYCEMIA

- Clinical signs of hypoglycemia will be monitored and documented.
- Hypoglycemic events will be treated using the existing treatment protocol (appendix) and will only be based upon glucometer values

CONTACTING DEXCOM

- Dexcom Technical Support information will be distributed to study personnel and contacted as needed. The contact information is as follows: [name] and [name].

DEXCOM CGM REMOVAL

- The CGM will remain in place for 7 days or until the patient is discharged.
- If it is thought that additional value would be gained from continuing use of the CGM for clinical care after 7 days, the CGM may be continued in an unblinded fashion, however the data collected will not be used for the purposes of the study.
- If the sensor should become dislodged at any time during the study period, it will be replaced using the same protocol. However, a new area of healthy skin will be chosen for sensor placement.
- At the end of the study time period, the sensor will be carefully removed by trained staff.
- Skin will be examined carefully and any changes to the skin associated with sensor use will be documented.

DATA ANALYSIS

Data collection

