Hypoglycemia was defined as a glucose concentration of <45mg/dL in order to correspond with the hospital's SOC protocol. Primary outcome measures were the number of hypoglycemic events detected by the sensor that were not detected by the hospital SOC. Secondary outcome measures were sensitivity, specificity, and positive predictive value of the device to detect hypoglycemia. When evaluating number of hypoglycemic episodes that occurred with each infant, the start of each hypoglycemic episode needed to be at least 60 minutes from the last episode to allow for treatment and resolution of hypoglycemia. A duration of 60 minutes was used to allow time for breast feeding in accordance with the nursery's SOC procedures (Supplementary Fig. S1). The CGM data were reviewed post hoc using Dexcom Studio Software. Using the Dexcom Studio Software to calculate the average CGM glucose level for each infant, a value of 39 mg/dL was used for all values that were reported as "low." All values reported by the CGM as "low" were excluded from the accuracy analysis. The mean absolute relative difference (MARD) was calculated by taking the absolute value of the difference between the CGM and hospital glucometer values and dividing by the hospital glucometer value individually, and then taking the mean of these values.

Additional outcome measures included CGM feasibility in the hospital setting. During the recruitment process and throughout the study, we asked caregivers for feedback about satisfaction with the CGM device. If any devices were removed before the end of the study period, we requested feedback from the families as well.

DATA COLLECTION SCHEDULE

Measurement	Study Entry	Daily	End of Study
Demographics	X		
Medical History (mother)	X		X
Medical History (infant)	X		X
Chart Review		X	X
Adverse Events		X	X
Nutrition		X	X
Glycemic Trends		X	X
Exam of skin site/sensor site	X	X	X

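### Read literally, the primary outcome counts sensor lows that a bedside test did not confirm, or that were never tested, as hypoglycemia missed by standard of care

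*Combined protocol and SAP*

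**What the plan says.** The Outcome measures section gives the primary outcome as follows: "Primary outcome measures were the number of hypoglycemic events detected by the sensor that were not detected by the hospital SOC". It defines hypoglycemia as a glucose concentration below 45 mg/dL, separates episodes by 60 minutes, and says that the CGM record was reviewed post hoc. It does not say whether a blood value must agree with the sensor.

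Blood testing after a sensor low appears elsewhere, as procedure:

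- **Summary:** "For each time point that the unblinded CGM group has a low blood sugar level, it will be verified by standard heelstick". I take the group named there to be the remotely monitored one.
- **Monitoring for hypoglycemia:** after an alert, the nurse first checks for pressure on the sensor. "If so, the infant may be repositioned and monitored to see if the glucose values rise above 45mg/dl". Then: "If CGM glucose values remain low, a bedside glucose reading will be performed".
- **Same section, alarm continuing a further 60 minutes:** "the nurse caring for the patient will be prompted to obtain an additional standard of care blood glucose measurement". The plan foresees that this test may disagree with the sensor: "If the measurement at 60 minutes shows that the patient has a BG >45mg/dl, the CGM may be re-calibrated".
- **Evaluation and treatment of hypoglycemia:** treatment of events "will only be based upon glucometer values".

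The Power calculation section says that the design was modified after recruitment fell short. The modified goal has two parts: whether CGM adds benefit by finding hypoglycemia that SOC testing missed, and how often CGM alerts are false positives.

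**The concern.** The primary outcome is meant to show what CGM finds that routine testing does not. That meaning depends on two terms that the outcome leaves open: what makes a sensor low a hypoglycemic event, and what counts as detection by SOC.

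If any sensor episode below 45 mg/dL qualifies, sensor error adds to the apparent benefit of the device. One alert could then support the first part of the goal as a missed event and enter the second part as a false positive. The false-positive rate and the positive predictive value describe sensor error, but they do not take it out of the primary count.

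If the alert-prompted test counts as SOC because the plan calls it that, a confirmed low has been detected by SOC and leaves the count, while unconfirmed and untested lows stay. The outcome would then measure nearly the opposite of what is intended.

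**Working it through.** The plan states no figure for this outcome, so there is none to reproduce. The check sorts sensor episodes below 45 mg/dL that have no routine SOC low and asks how each reading treats them.

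| Episode | All-sensor (literal) | Confirmed only | Prompted test treated as SOC |
|---|---|---|---|
| Prompted test below 45 mg/dL | counts | counts | drops out |
| Prompted test 45 mg/dL or above | counts | does not count | counts |
| Remote group, resolved on repositioning, no test | counts | does not count | counts |
| CGM-alone infant, no glucometer value during the episode | counts | does not count | counts |
| Found only at later review, no matching value | counts | does not count | counts |

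Each row can arise under the plan:

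- Row 2 is foreseen by the re-calibration rule, which does not say that the event is then removed from the count.
- Row 3 follows from making the bedside test conditional on the sensor staying low. This is narrower than the Summary's promise to verify every low.
- Row 4 follows because alerts and prompted tests are described only for remote monitoring.
- Row 5 follows from the post hoc review, when an untested low can no longer be checked.

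Let C, N and U be the numbers of confirmed, not-confirmed and untested episodes, with confirmation by prompted test. The three columns count C + N + U, C, and N + U.

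An example shows how far these can separate. **Every input is assumed:** 20 such episodes, a tested share t of 25% to 75%, and a confirmed share c among those tested of 25% to 75%. Then C = 20·t·c.

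- All-sensor: 20.
- Confirmed only: from 20 × 0.25 × 0.25 = 1.25 to 20 × 0.75 × 0.75 = 11.25.
- Prompted test treated as SOC: 20 − C, so from 20 − 11.25 = 8.75 to 20 − 1.25 = 18.75.

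The spread reflects the assumed shares as well as the choice of rule. It illustrates the ambiguity and does not estimate its effect in this study.

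Two further points bear on whether other analyses fill the gap. Readings that the device displays only as low are excluded from the accuracy analysis, with no stated exclusion from the event count, so that analysis does not check them. Calibration tests also need a stated status: the plan has clinical staff told when a calibration value is below 35 mg/dL, so a test done for the study can enter care.

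**The case against.** The strongest reply is that the plan already treats the glucometer as the truth. Hypoglycemia is a glucose concentration, not a sensor reading. Treatment follows the glucometer, the Summary promises heelstick verification, and sensitivity, specificity and predictive value all need a reference standard. A plan that names false positives hardly means to count them as hypoglycemia. The standard-of-care label may describe only the kind of test, as distinct from the study glucometer used for calibration. This makes the confirmed-only reading plausible, and I accept it as a possible intent. But the outcome does not adopt it, and no section links verification to the count.

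Other parts of the reply stand and limit the point:

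- A reader might infer that a bedside value of 45 mg/dL or above proves the sensor wrong. It does not. The test comes after contact, assessment and possibly repositioning, and glucose may have changed. Such an episode is not confirmed, which is weaker than refuted.
- A reader might take the re-calibration trigger, "For all blood glucose measurements that are >20% different from the Dexcom CGM values in the experimental group", as an accuracy tolerance and derive from it how many events are misclassified. It only permits an early re-calibration. Two imperfect measures can fall on either side of a cutoff in both directions, and the trigger does not say how often.
- Calibration values are entered into the device, so they are not fully independent of it.
- Counting confirmed episodes alone would hide untested lows in CGM-alone infants, which may be the very lows that SOC misses. The choice between the counts is partly a choice of estimand.
- It is unclear whether the two-arm structure still governs the modified analysis. The SOC algorithm in the appendix is not reproduced in the text available, so the routine testing schedule could not be checked.

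**Conclusion.** The point holds as an ambiguity in the primary outcome with a real consequence. Applied as written, the definition credits unconfirmed and untested sensor lows as hypoglycemia missed by SOC. One possible reading of the standard-of-care label would also remove confirmed ones.

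A reader might go further and conclude that the plan deliberately counts false positives, or that the primary result is inflated by a known amount. The documents support neither. They do not say which reading was used, and they give no event counts, tested share or confirmation rate, so the number of affected episodes cannot be estimated.

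The conclusion rests on the outcome wording and on no other section supplying the rule. The points about CGM-alone infants apply only so far as that arm remains in the modified design. This is a cheap improvement: it clarifies what the primary number means and leaves study conduct unchanged.

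**What to change.** In the Outcome measures section:

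1. State that a test prompted by a CGM alert, or done only for calibration, is not SOC detection.
2. Name the reference glucometer values and a matching window around each sensor episode.
3. Keep the all-sensor count, and split it using values already collected: confirmed (a matched value below 45 mg/dL), not confirmed (all matched values 45 mg/dL or above), and untested (no matched value).
4. Rest the claim of additional benefit on confirmed episodes with no SOC low. Show not-confirmed and untested episodes beside it, by monitoring group where the arms still apply, because only remotely monitored infants have alert-prompted tests.
5. Flag matches that rest only on calibration values, and note that a value of 45 mg/dL or above after a delay or repositioning does not prove sensor error.
6. If the data were already reviewed, as the past tense of this section suggests, label the split post hoc.

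The cost is revised wording and a relabelling of existing values, with no new tests and no change to care. The downside is a smaller headline count, with few confirmable episodes in CGM-alone infants. Keeping the untested column in view limits that loss.
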